14.3 Outcome Measures

14.3.1 Primary Efficacy Endpoint

- The primary metric for analysis will be change in mean CGM between the second last 7 days week
- of the control Usual-Care period and the one-week Remote Monitored At-Home FCL period.

1154 **14.3.2 Secondary Outcomes**

- Glycemic Metrics will be obtained directly from CGM data and will include the standard metrics
- recommended by the international consensus on CGM including mean CGM, GMI derived from
- mean CGM, time in range 70-180 mg/dL, CGM standard deviation (StDev), CGM coefficient of
- variation (CV), CGM %<54 mg/dL, CGM %<70 mg/dL, CGM %>180 mg/dL, and CGM %>250
- 1159 mg/dL. For the Usual Care period, CGM data will be obtained from either the participant's
- personal CGM or a study provided CGM. Data for the control Usual-Care period will be analyzed
- by last available 7-day period. During the FCL period, CGM data will be obtained directly from
- the study device. As GMI is a linear transformation of mean CGM, this metric will have the same
- effect and will be presented as a primary outcome as well. All other glycemic metrics will be
- 1164 considered secondary outcome measures.
- Device-Use Metrics will include time in automation, total daily insulin dose, and number of
- boluses per day. During the Usual Care period, participants using an insulin pump will have their
- pump uploaded at the end of the period to capture their insulin delivery and bolus data. The FCL
- period, insulin use, and bolus data (if any) will be captured from the experimental device.
- Exercise Challenge Metrics will include the duration of exercise, approximate intensity of exercise
- (low, moderate, or high intensity), the % CGM<70 mg/dL, % CGM<54 mg/dL, and any episodes
- of SH (CGM<70mg/dL for more than 15 minutes with interruption, CGM≥70, of less than 15
- minutes or CHO treatment) during and 2 hours after the exercise challenges.
- 1173 Unannounced Meal Metrics during the supervised house/hotel FLC stage participants will be
- instructed to eat at least 3 meals per day. The time of completion for these meals will be recorded
- by study staff. The % CGM>250 mg/dL for the 4 hours after each meal will be recorded and
- specifically analyzed. Participants will be instructed to freely eat meals during the supervised at-
- home FCL stage but will not be required to record the timing of the meals for unannounced meals.
- Patient Reported Outcomes will include several surveys aiming to capture participant satisfaction
- 1179 with the FCL device and any changes in distress or burden of diabetes management. See
- 1180 APPENDIX for survey tools. These surveys will include:

MiniNET 25-Oct-2024 Page 52 of 60

1181	a. The INSPIRE Measures: A validated tool assessing the positive expectancies of AID
1182	systems for youth, adults, and parents and partners of people with diabetes. This tool
1183	has been specifically endorsed by the FDA for use with developing insulin-dosing
1184	systems.
1185	b. Technology Expectations Surveys: A 25 question self-report measure of
1186	expectations from advanced technologies and perceived impact of the technology on
1187	quality of life. Validated to age 13+ years.
1188	These surveys will be administered at baseline and then at the end of the prior to or at the start of
1189	the 1-week supervised House/Hotel FCL period and at the end of the 1-week remote-monitored
1190	at-home FCL study
1191	14.3.3 CGM Data Treatment
1192	a. Saturated CGM values "High" and "Low" will be replaced by 401mg/dL and
1193	39mg/dL respectively.
1194	b. Any CGM gaps shorter than 1 hour will be interpolated
1195	c. CGM data during recorded occlusion event will be removed from analysis as
1196	follows: any measurement less than 2h before or after the time of record will be
1197	removed.
1198	d. CGM data following a pump/DiAs communication interruption >1h by less than 2h
1199	will be removed
1200	14.3.4 Outcome Computation Conditions
1201	Outcomes will only be computed if at least 80% of the analysis window CGM measurements (after
1202	data treatment) are available.
1203	14.4 Safety Analyses
1204	We will assess for the system's functionality, including the ability of the system to run its code
1205	without error (delivering insulin safely, as planned), as well as its ability to avoid low BG <70
1206	mg/dL.
1207	14.5 Baseline Descriptive Statistics
1208	Baseline demographic and clinical characteristics of the cohort of all randomized participants will
1209	be summarized in a table using summary statistics appropriate to the distribution of each variable.
1210	Descriptive statistics will be displayed overall and by treatment group.
1211	Will include:
1212	a. Age
1213	b. HbA1c
1214	c. Gender

MiniNET_25-Oct-2024 Page 53 of 60

5	d. Race/ethnicity
6	e. CGM use before enrollment
7	f. AID use before enrollment
8	g. Diabetes duration
9	h. BMI
0	i. Total Daily Insulin
1	14.6 Device Issues
2	The following tabulations and analyses will be performed during time on the UVa AP systems to
3	assess device issues:
4	a. Device malfunctions requiring study team contact and other reported device issues
5	b. % time CGM data available
6	c. % time with closed loop control

MiniNET_25-Oct-2024 Page 54 of 60

1227 Chapter 15: Data Collection and Monitoring

1228 **15.1 Case Report Forms and Device Data**

- The study data are collected through a combination of case report forms (electronic and paper) and
- 1230 electronic device data files obtained from the software and individual hardware components.
- 1231 These electronic device files and electronic CRFs are considered the primary source
- 1232 documentation.
- 1233 When data are directly collected in electronic case report forms, this will be considered the source
- 1234 data. Records will be maintained in accordance with ICH E6 and institutional regulatory
- requirements for the protection of confidentiality of participants.

1236 **15.2 Study Records Retention**

- 1237 Study documents should be retained for a minimum of 2 years after the last approval of a marketing
- application in an ICH region and until there are no pending or contemplated marketing applications
- in an ICH region or until at least 2 years have elapsed since the formal discontinuation of clinical
- development of the investigational product. These documents should be retained for a longer
- period, however, if required by local regulations. No records will be destroyed without the written
- 1242 consent of the sponsor, if applicable. It is the responsibility of the sponsor to inform the
- investigator when these documents no longer need to be retained.

1244 **15.3 Protocol Deviations**

- 1245 A protocol deviation is any noncompliance with the clinical trial protocol, Good Clinical Practices
- 1246 (GCP), or procedure requirements. The noncompliance may be either on the part of the participant,
- the investigator, or the study site staff. As a result of deviations, corrective actions may be
- developed by the site and implemented as appropriate. Major deviations will be reported to the
- 1249 IRB-HSR within 7 calendar days of when the study team becomes aware of the event.

MiniNET 25-Oct-2024 Page 55 of 60

Chapter 16: Ethics/Protection of Human Participants

1251 16.1 Ethics Standard

1255

1262

1263

1264

1265 1266

1267

1268

1269

1270

1271

1272

- 1252 The investigator will ensure that this study is conducted in full conformity with Regulations for
- the Protection of Human Participants of Research codified in 45 CFR Part 46, 21 CFR Part 50, 21
- 1254 CFR Part 56, and/or the ICH E6.

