All key personnel (all individuals responsible for the design and conduct of this trial) have completed Human Participants Protection Training and Good Clinical Practice Training. Further, I agree to ensure that all staff members involved in the conduct of this study are informed about their obligations in meeting the above commitments.

Investigator's Signature	Date:	/	/	
Investigator's Name:				
Site Name: University of Virginia				

MiniNET 25-Oct-2024 Page 4 of 60

LIST OF ABBREVIATIONS

Abbreviation	Definition
ADA	American Diabetes Association
AE	Adverse Event
AID	Automated insulin delivery
AIDANET	Automated insulin delivery as Adaptive Network
AP	Artificial pancreas
AUC	Area Under the Curve
AYA	Adolescent and Young Adult
BDC	Barbara Davis Center
BG	Blood Glucose (as assessed by a blood glucose meter)
BGM	Blood glucose meter
CGM	Continuous glucose monitor
CSII	Continuous subcutaneous insulin infusion
DiAs	Diabetes Assistant
DKA	Diabetic Ketoacidosis
FCL	Fully closed loop
HbA1c	Hemoglobin A1c
HCL	Hybrid closed loop
JDRF	Juvenile Diabetes Research Foundation
MDI	Multiple daily injections
NAP	Neural network artificial pancreas
SAE	Severe Adverse Event
SG	Sensor Glucose (as assessed by a continuous glucose monitor)
SH	Severe Hypoglycemia
T1D	Type 1 diabetes
TAR	Time above range
TBR	Time below range
TIR	Time in range 70-180 mg/dL

MiniNET_25-Oct-2024 Page 5 of 60

PROTOCOL SUMMARY

Participant Area	Description
Title	Safety and Feasibility Testing of a Smaller Network Version of AIDANET
Investigational Device	AIDANET algorithm as smaller network version with DiAs phone, Tandem t:AP insulin pumps, and Dexcom CGM
Objectives	The primary objective of the project is to demonstrate feasibility and safety of the Automated Insulin Delivery as Adaptive NETwork (AIDANET) system run in a new smaller network version, used in full closed loop (FCL) by adults with T1D.
Study Design	Randomized crossover, device safety/feasibility supervised house/hotel with transition to home use, interventional trial of AIDANET
Number of Sites	1
Endpoint	The primary metric for analysis will be change in mean CGM between the week of the control usual-care period and the one-week Remote Monitored At-Home Full Closed Loop period using AIDANET.
Population	 Key Inclusion Criteria Age 18-60 years at time of consent. Clinical diagnosis of T1D, based on investigator assessment, of at least 1 year duration.
Sample Size	Complete 6 participants

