2.4.2 Exercise Testing

During the supervised hotel period, participants will engage in mild activity (a walk of approximately 30 minutes) on Day 2. Study staff will set a Temporary Control Rate (TCR) of approximately 50-100% starting up to approximately one hour prior to exercise for approximately 2 hours, actual TCR settings will be tailored to an individual person. Study staff will record the duration, approximate intensity (low, moderate, or high intensity), the TBR <70 mg/dL, TBR <54 mg/dL, and any episodes of Severe Hypoglycemia (SH) during the walk and in the 2 hours after the exercise challenges. Participants will be provided with an exercise monitor (e.g., Fitbit) for use during the control and FCL periods. Participants will be allowed to practice their usual exercise routine during the control and remote-monitored at-home FCL periods with use of the TCR as needed. They will not be required to record exercise events during these periods.

MiniNET 25-Oct-2024 Page 17 of 60

2.5 Study Devices Download Data from the study devices will be captured in real-time by the remote monitoring server for the

- 212 DiAs system. In addition, study devices will be downloaded at the end of the Remote-Monitored
- 213 At-Home FCL period.
- 214 **2.6 Study System Issues**
- 215 If the CGM signal becomes unavailable for more than 20 minutes consecutively, closed loop will
- 216 not operate to automatically adjust insulin delivery. If the CGM is not connected, the system will
- revert to the usual open loop function of the pump and deliver insulin with the pre-programmed
- dosing parameters. Resumption of closed-loop control will occur automatically once the CGM
- signal is again available.
- 220 If the DiAs system is unable to maintain connectivity with the Tandem t:AP pump, the pump will
- automatically revert to the pre-programmed dosing parameters after 30 minutes without any need
- for interaction from the user.

MiniNET 25-Oct-2024 Page 18 of 60

223 Chapter 3: Study Screening

- 224 **VISIT 1**
- 225 3.1 Clinical Site
- The study will be performed at the University of Virginia. Screening procedures will be performed
- either virtually or on site, at a clinical research unit, or at the hotel.
- 228 **3.2** Participant Recruitment and Enrollment
- We will enroll up to 12 participants who have been diagnosed with type 1 diabetes for at least one
- 230 year. This enrollment number accounts for dropouts or screen failures that may occur. The goal is

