7.6.1 Hypoglycemia

- a. If CGM falls below 70 mg/dL at any time, confirm <70mg/dL CGM readings and potential hypoglycemia symptoms with a fingerstick blood glucose. If blood glucose confirms <70mg/dL CGM reading, hypoglycemia will be treated with oral glucose of approximately 5-15 g. Participants will be encouraged to wait 15 min prior to giving a second glucose treatment. These fingerstick checks will be performed during the hotel stay and during the home portion if the participant chooses to do so. During the hotel stay we will also recheck a fingerstick blood glucose before retreatment.
- b. If a participant experiences any symptoms of hypoglycemia (e.g., shakiness, dizziness, sweating, pallor, clumsiness, difficulty paying attention, or tingling around the mouth), then the participant should treat with oral glucose of 5-15 g. Participants will be encouraged to wait 15 min prior to giving a second glucose treatment. During the hotel portion of the study, a fingerstick blood glucose will be assessed before such treatment for symptoms and before any re-treatment.
- c. If a participant displays any signs of neuroglycopenia (e.g., lethargy, disorientation, confusion, or inappropriate behavior) or severe hypoglycemia (e.g., hypoglycemic seizure, loss of consciousness, inability to properly consume treatment) hypoglycemia will be treated with either oral glucose or glucagon. The patient will be discharged from the study. The participant should consult with a study physician to discuss next steps for broader evaluation of symptoms unrelated to hypoglycemia.

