12.2 Reportable Events

For this protocol, a reportable adverse event includes any untoward medical occurrence that meets one of the following criteria:

- A serious adverse event as defined in section 12.1.2.
- An Adverse Device Effect as defined in section 12.1.4, unless excluded from reporting in section 12.7.
- An Adverse Event as defined in section 12.1.1 occurring in association with a study procedure.
- An AE as defined in section 12.1.1 which leads to discontinuation of a study device for 4 or more hours during the hotel phase and 12 or more hours during the at home phase.
- Hypoglycemia meeting the definition of severe hypoglycemia as defined in section 12.2.1
- Diabetic ketoacidosis (DKA) as defined in section 12.2.2 or in the absence of DKA, a hyperglycemic or ketosis event meeting the criteria defined below.

Hypoglycemia and hyperglycemia not meeting the criteria below will not be recorded as adverse events unless associated with an Adverse Device Effect. Skin reactions from sensor placement are only reportable if severe and/or required treatment.

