12.2.1 Hypoglycemia Event

Hypoglycemia not associated with an Adverse Device Effect is only reportable as an adverse event when the following definition for severe hypoglycemia is met:

- The event required assistance of another person due to altered consciousness, and required another person to actively administer carbohydrate, glucagon, or other resuscitative actions.
- Impaired cognitively to the point that he/she was unable to treat himself/herself, was unable to verbalize his/ her needs, was incoherent, disoriented, and/or combative, or experienced seizure or coma. These episodes may be associated with sufficient neuroglycopenia to induce seizure or coma.
- If plasma glucose measurements are not available during such an event, neurological recovery attributable to the restoration of plasma glucose to normal is considered sufficient evidence that the event was induced by a low plasma glucose concentration.

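### Section 14.3.2 labels a CGM-defined low in the exercise window as SH (severe hypoglycemia), which contradicts the clinical definition in 12.2.1; a minor error, confined to one secondary metric

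*Combined protocol and SAP*

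**What the plan says.** The abbreviation list expands SH as "Severe Hypoglycemia". Section 2.4.2 uses it in that sense for the exercise test, where staff are to record "any episodes of Severe Hypoglycemia (SH) during the walk and in the 2 hours after the exercise challenges". It gives no criterion and no cross-reference.

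Section 14.3.2, under Exercise Challenge Metrics, lists the same item for the same window but attaches a sensor rule: "of SH (CGM<70mg/dL for more than 15 minutes with interruption, CGM≥70, of less than 15". The rule closes by allowing for carbohydrate treatment and naming the walk and the 2 hours after it as the window.

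Section 12.2.1 defines severe hypoglycemia by clinical state. One element is "The event required assistance of another person due to altered consciousness", with that person actively giving treatment. Another is "Impaired cognitively to the point that he/she was unable to treat himself/herself", which extends to seizure or coma. Section 7.6.1(c) uses the term in the same way, with seizure, loss of consciousness and inability to take treatment as its examples.

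A reading below 70 mg/dL is an ordinary low elsewhere in the protocol. Under 7.6.1(a), once a fingerstick confirms it, "hypoglycemia will be treated with oral glucose of approximately 5-15 g". Section 12.2 says: "Hypoglycemia and hyperglycemia not meeting the criteria below will not be recorded as adverse events unless associated with an Adverse Device Effect". Section 14.4 refers to such values simply as low BG.

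**The concern.** One term carries two definitions for the same event in the same 2.5-hour window, and no text reconciles them. Neither definition contains the other, so they can disagree in both directions. A self-treated sensor low can count as SH in the exercise table and be absent from the adverse event listing. An assisted event with only a short sensor low can appear in the listing and be absent from the exercise table.

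Staff working from 2.4.2 have the label without the sensor rule, while the analyst working from 14.3.2 has the sensor rule. The staff record and the analysis can therefore differ under one name. In a safety and feasibility study, severe hypoglycemia is a term that readers take literally, so its counts should agree wherever they are reported.

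**Working it through.** The plan states no figure to reproduce. The check sets the two definitions side by side and applies them to the same episodes.

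**Inputs**
- Window: a walk of about 30 minutes (2.4.2, 7.5) plus the following 2 hours (2.4.2, 14.3.2): 30 + 120 = 150 minutes.
- Rule in 14.3.2: CGM below 70 mg/dL for more than 15 minutes, with a clause on interruptions of less than 15 minutes or carbohydrate (CHO) treatment. No symptom or fingerstick confirmation is required.
- Rule in 12.2.1: clinical state only, with no sensor threshold or duration.
- Exposure: one scheduled walk (Day 2 of the hotel stay) and a target of 6 completers (14.2).

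**Size of the window**
- Shortest low that meets the stated duration: just over 15/150 = 10.0% of the window.
- Total exposure: 6 × 150 = 900 minutes = 15 hours.

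**The CHO clause can be read in three ways**
- (i) CHO treatment ends an episode.
- (ii) CHO treatment is a tolerated interruption.
- (iii) CHO treatment itself qualifies an episode.

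**Episode A: CGM at 65 mg/dL for 20 minutes, no impairment, treated by the participant or not treated.** CGM below 70 mg/dL is 20/150 = 13.3% of the window, and CGM below 54 mg/dL is 0/150 = 0%.
- 12.2.1: not severe hypoglycemia.
- 14.3.2, no CHO taken: SH, since 20 minutes exceeds 15.
- 14.3.2, CHO taken at minute 10: not SH under (i), because the episode closes at 10 minutes; SH under (ii) and (iii).

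**Episode B: CGM below 70 mg/dL for 10 minutes, no impairment, self-treated with oral glucose.**
- 12.2.1: not severe hypoglycemia.
- 14.3.2: not SH under (i) or (ii), since 10 minutes is below the limit; SH under (iii).

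**Episode C: altered consciousness, another person gives treatment, CGM below 70 mg/dL for 10 minutes.**
- 12.2.1: severe hypoglycemia.
- 14.3.2: not SH under (i) or (ii); SH under (iii) only if the treatment was carbohydrate.

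**Result.** Under every reading of the clause, at least one ordinary low is scored as SH: Episode A without CHO suffices. Under every reading, some event that is severe by 12.2.1 can go uncounted: Episode C treated with glucagon suffices. The mismatch therefore does not depend on how the clause is read, but the score of a given treated low does.

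No expected number of such episodes can be given. The documents state no rate, and the requirement of at least 80 mg/dL to start the walk (7.5), the Temporary Control Rate (2.4.2) and supervised treatment (7.6.1) should keep lows few.

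**The case against.** The best defence is that the parenthesis in 14.3.2 is an operational definition. It stands beside the label, so the analyst has a rule and a reader can see what was counted. The other glycemic items in that line (percent of CGM below 70 and below 54 mg/dL) are also sensor-based, and 14.1.1 already foresees a count of hypoglycemia among the secondary outcomes. SH is then most simply a labelling slip. The metric is secondary, Table 2 lists only percent below 70 mg/dL for exercise, and the safety analysis in 14.4 does not rest on an SH count.

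Most of this stands, and it is why the point is minor. It does not remove the contradiction. If a sensor-defined episode is intended, the label is wrong, because both the abbreviation list and 2.4.2 fix the meaning of SH, and 2.4.2 does so for this same window.

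A reader might infer more: that the label misstates the device's safety record, or that two exercise SH episodes would meet, or seem to meet, the rule for suspending the study. The documents do not support that. The two-event severe hypoglycemia rules in 12.9.1 and 12.9.2 cite 12.2.1 expressly. Adverse event reporting under 12.2 uses the same definition. The Medical Monitor reviews each adverse event form (12.2.2) and every severe hypoglycemia event as it occurs (12.10). Confusing the two counts would mean overlooking both the printed sensor criterion and those cross-references.

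**Conclusion.** Wrong as written, and minor. Section 14.3.2 gives the name severe hypoglycemia to a sensor finding that 12.2.1 and 7.6.1(c) do not treat as severe. Taken literally, the exercise table could show SH episodes that the adverse event listing does not, and could omit a brief assisted event that the listing does show.

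The effect is limited to one secondary metric over about 15 hours of exercise windows in 6 completers. The primary endpoint, adverse event reporting and the stopping rules do not change. The mismatch is certain from the text. How often it would appear is unknown, and the score of any treated low depends on a CHO clause that the plan leaves open.

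**What to change.** In 14.3.2:
- Rename the item *CGM-measured hypoglycemia episode (below 70 mg/dL for more than 15 minutes)*.
- State whether CHO treatment ends an episode, is a tolerated interruption, or itself qualifies an episode. Renaming alone would leave the count open to different scoring.
- Report SH in the exercise window as a separate item, limited to events that meet 12.2.1.

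In 2.4.2, add a cross-reference to 12.2.1 where SH is mentioned. Staff already record time below 70 mg/dL, time below 54 mg/dL and SH as separate items there, so nothing else need change.

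The cost is a wording amendment with IRB approval under 16.2. It adds no procedure, visit or data collection.
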